### **19.2. Plan for Reporting Adverse Events**

Serious adverse events will be reported immediately to the Principal Investigator (PI), who will immediately notify all other investigators. The PI will file a full written report to the OHSU Institutional Review Board (IRB) within 24 hours of notification of the serious event, as required by the OHSU IRB. Specifically, the following will be reported, in writing: 1) all deaths in study participants, during the intervention period, regardless of cause, 2) all serious adverse events associated with the study procedures

Moderate adverse events will be tabulated by the PI, who will notify members of the research team if trends are identified. If trends are noted, preventive measures will be implemented, such as providing education of participants in the study to emphasize prevention of the adverse event. Moderate adverse events will be included in annual reports to the OHSU IRB.

Mild adverse events will not be formally logged but, participants will receive advice on avoiding such events.

Unexpected adverse events that do not include physical harm, usually having to do with study procedures, will be reported within 10 days to OHSU IRB, using a written report form.

Adverse events will be reported to NIH according to NIH protocols.

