Interested participants will be screened either by phone or in person using an IRB approved screening script. After initial screening, potentially eligible men will be scheduled for consent and baseline screening and possible further baseline testing in qualified men. Screening includes review of fall history in the past year, a 3-meter Timed Up and Go walk at usual pace, and standing up and down from a chair five times as fast as safely possible. The testing session will include DXA, performance testing and survey completion and will be repeated at 3- and 6-mos. (post-intervention), and 6 mos. after completion of the intervention (follow-up). Total time for performance testing and survey completion is ~2-2.5 hours. Men will complete written surveys on a computer at baseline and online for follow-up visits, unless they prefer to complete paper surveys. Staff will review surveys for completeness and follow up with participants in person or by phone on missing data. To reduce bias we will retain blinding of the research assistants who conduct the testing visits, by having the Project Director provide each participant with an envelope that contains his random group assignment *after* baseline testing is complete. Qualified men will

be randomly assigned to 1 of 3 groups: 1) tai ji quan, 2) strength training or 3) stretching control. To avoid confounding and differential tolerance to exercise by ADT history and age, block randomization stratifying for timing of ADT (past or current) and will be done using EXCEL to generate random assignments from each block. Assignment will be in random blocks of 6 to 9 within each wave (~42-48 men) to facilitate even enrollment and to prevent the Project Director from predicting group assignment.

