## **9.0 DATA AND SPECIMENS (REQUIRED)**

### **a) Handling of Data and Specimens**

All contact information collected from the study, including name, mailing address, phone number and email address, will be stored on an encrypted and password protected computer drive in the OHSU Knight Cancer Research Building that only IRB approved persons have access to.

All other data collected for this study including answers from the health history form (e.g. DOB, education, income, demographics, as well as cancer specific information such as diagnosis, type & dates of cancer treatments), answers to the study surveys, and results from the physical tests will be stored in OCTRI's installation of REDCap, a highly secure and robust web-based research data collection and management system.

Data that may be collected from a patient's electronic medical record would include contact information including phone number, mailing address and email address, as well as cancer specific information such as diagnosis, type & dates of cancer treatments. Any data collected will be stored on an encrypted and password protected computer drive in the OHSU Knight Cancer Research Building that only IRB approved persons have access to.

Consent forms and any surveys that were filled out on paper will be stored in a locked cabinet in a locked, secure room in the OHSU Knight Cancer Research Building.

Data from the HHQ, surveys and physical tests will be transported by secure electronic transmission (i.e. secure, encrypted email or stored on a secure shared drive such as Box).

The PI will be responsible for the receipt or transmission of the data.

Data will be stored until data analysis is complete and then the data will be transferred to a repository.

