### **b. Protection Against Risk**

**Participant safety and side effects during exercise.** As with any form of exercise, there is a slight risk of injury. We have not had a single participant drop out of a study due to an injury related to the exercise program; however, as with any study in older adults, exercise adherence has been affected by minor musculoskeletal complaints and are typically exacerbations of pre-existing orthopedic conditions. We will take the following steps to reduce the risk of injury and symptoms/side from exercise training: 1) Physician clearance: We will send a notice to each participant's oncologist (or primary care provider) asking him or her to clear the participant for participation in physical performance testing and any of the study exercise programs prior to beginning exercise training. If a man's physician does not clear him for participation we will inform the participant and refer him to her physician for clarification of the decision, 2) Monitor for and treat early musculoskeletal symptoms: From experience in our prior trials we have developed an

injury prevention education and monitoring program. At the beginning of each participant's start in the intervention he is provided general injury prevention information from the Project Director and exercise trainer. During the intervention the exercise trainer will consult with the Project Director on any reported exercise-related injuries and/or physical complaints from participants that affects their ability to do their exercise program. The Project Director will consult with participants on an individual basis, as needed, and will advise on treatment of their injury/complaint and when referral to a health practitioner is appropriate. The Project Director will work with the study team to track minor and major complaints and injuries in order to evaluate the overall safety and appropriateness of the study interventions for the study population.

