### **19.1 Monitoring Plan:**

This study represents a moderate risk to study participants because it is a clinical trial involving human subjects. Though physical activity and exercise may be associated with adverse events (e.g. tiredness, muscle soreness, muscular injury, cardiac events, shortness of breath), most such events are associated with inappropriately vigorous exercise, which is not the objective of this study. The study will be wholly overseen by the OHSU NCI-designated Comprehensive Cancer Institute for both safety and compliance to institutional and NCI policies. The PI is responsible for evaluating each adverse event as it occurs and for notifying the OHSU IRB of the occurrence of an adverse event according to IRB protocols. An interim safety review will occur early in the intervention period to determine potential safety concerns before the total sample has been accrued. The interim safety review will be overseen by OHSU Knight Data Safety and Monitoring Committee (DSMC, see details below) and will occur after the first 45 enrolled men (~1/8th of total sample) have completed 3 months of exercise training to assess early for program safety.

Adverse events related or possibly related to exercise sessions (i.e., group exercise classes, prescribed home program exercise, and physical performance measurement appointments) will be graded according to their significance for severe consequences, such as injury or death, using the following grades determined by the OHSU IRB.

Examples of serious adverse events (life-threatening or disabling and requiring medical attention). Serious adverse events that may occur during exercise in this study include death and cardiovascular events, though these are extremely rare in the absence of significant cardiac pathology.

Examples of moderate adverse events (resolve with treatment). Moderate adverse events that may occur during exercise include symptoms, such as shortness of breath and orthostatic intolerance.

Examples of mild adverse events (do not require treatment). Reports of side effects, such as muscle soreness, moderate tiredness while exercising, and similar discomforts are mild adverse events.

Examples of unexpected adverse events that do not include physical harm. Adverse events can also include breaches of confidentiality, emotional harms, or complaints about study procedures or conduct of investigators.

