In this study we do not anticipate moderate or serious adverse events. Only moderate and serious adverse events that are related or possibly related to exercise sessions (i.e., group exercise classes, prescribed home program exercise, and physical performance measurement appointments) will be reported on our Adverse Events Log.

A survey (Adverse Events Survey) was created by the study team to be administered monthly during the participants' year long participation in the study. Adverse events reported through this survey may be followed-up by study staff with a phone call, e-mail, or in person in class during the intervention period, when participants self-report that their reporting condition is due to a study-related exercise activity or if more information is needed to determine reportability. Participants will also have the opportunity to report adverse events during exercise class or at physical performance measurement appointments.

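### The adverse-event record that is logged and tabulated leaves out mild events and is filtered on relatedness to exercise, and no harms table by randomised arm is planned

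*Combined protocol and SAP*

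**What the plan says.** Section 19.1 sets the scope of the Adverse Events Log: "Only moderate and serious adverse events that are related or possibly related to exercise sessions" are entered. Exercise sessions there cover classes, prescribed home exercise and performance-testing appointments. The same section grades the commonest expected effects as mild: "Reports of side effects, such as muscle soreness, moderate tiredness while exercising, and similar discomforts are mild adverse events". It also says that the team does not anticipate moderate or serious events.

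Section 19.2 then says: "Mild adverse events will not be formally logged but, participants will receive advice on avoiding such events". For the next grade up: "Moderate adverse events will be tabulated by the PI, who will notify members of the research team if trends are identified". Arm is not mentioned.

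A monthly Adverse Events Survey runs through each man's year (Section 8.0, Schedule of Events; Section 19.1). Staff may follow up a survey report "when participants self-report that their reporting condition is due to a study-related exercise activity", or when they need more information to decide reportability.

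Section 10.0, Protection Against Risk, goes further. There the Project Director is given this task: "track minor and major complaints and injuries in order to evaluate the overall safety and appropriateness of the study interventions for the study population". No form or data set is named for this.

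Section 13.0 contains no adverse-event summary or comparison. Its only harm-related analysis is of injurious falls, under Additional Analyses.

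**The concern.** The trial compares weighted-vest strength training, tai ji quan, and seated or lying stretching. A clinician choosing among them needs their harms on the same basis as their benefits. The record that the plan tabulates cannot supply this, for two reasons.

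First, it covers the grades that the team does not expect and leaves out the grade that it does. Second, it is filtered on relatedness, and that judgement draws partly on what men report. They are not blinded: the plan describes "having the Project Director provide each participant with an envelope that contains his random group assignment". A sore knee may be easier to blame on a weighted vest than on a stretching class, so a count filtered in this way is not a neutral basis for comparing arms.

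What is at stake is the comparative account of harm. The falls, frailty and function analyses are untouched.

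**Working it through.** The plan gives no adverse-event rate and no figure to reproduce. The main check is therefore to follow each kind of event through the text.

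| Event | Where it goes | Comparison by arm planned |
|---|---|---|
| Mild, exercise-related | Not formally logged (19.2) | None |
| Moderate, at least possibly exercise-related | Log; tabulated for trends; annual IRB report (19.1, 19.2) | None stated |
| Serious, at least possibly exercise-related | Log; written IRB report (19.1, 19.2) | None stated |
| Death during the intervention, any cause | Written IRB report (19.2) | None stated |
| Unexpected, no physical harm | IRB report within 10 days (19.2) | None stated |
| Other event unrelated to exercise | Not logged; seen only if reported on the survey | None |
| Falls | Monthly reports, confirmed by phone (3.0) | Yes, primary endpoint |
| Injurious falls | Recorded at the same call (3.0) | Logistic regression among fallers (13.0) |

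Beyond falls, no row leads to a comparison by arm, and the first row has no formal record.

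**Is the information collected?** Probably. Section 9.0 says that "answers to the study surveys, and results from the physical tests will be stored in" the REDCap system, and the Adverse Events Survey is a study survey. The survey items are not shown, so whether it captures mild soreness, or yields countable events, is unknown. The planned volume is 120 × 6 = 720 monthly surveys per arm in months 1-6 and 120 × 12 = 1,440 over the year, before attrition and non-response.

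**What precision would a by-arm table have?** Inputs: n = 120 per arm (Section 13.0), or 284/3 = 94.7, taken as 95, if the N=284 in Section 4.0 is the enrolled total split evenly (an assumption). The proportion p of men reporting any event is assumed to be 30% to 50% in both arms. The 95% half-width for a risk difference is 1.96 × √(2p(1−p)/n).

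- n = 120, p = 0.30: 1.96 × √(0.42/120) = 11.6 points
- n = 120, p = 0.50: 1.96 × √(0.50/120) = 12.7 points
- n = 95, p = 0.30: 1.96 × √(0.42/95) = 13.0 points
- n = 95, p = 0.50: 1.96 × √(0.50/95) = 14.2 points

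**How much does counting every cause dilute a difference?** Suppose a background event risk b, the same in each arm and independent of exercise-related events. The risk of any event is then 1 − (1−e)(1−b), where e is the exercise-related risk, so a true difference in e shrinks by the factor (1−b). At an assumed b of 30% to 50%, a 15-point difference becomes 15 × 0.70 = 10.5 down to 15 × 0.50 = 7.5 points. The any-event table therefore removes the attribution filter at the price of a smaller visible difference. That is why a graded table is needed beside it.

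**The case against.** The strongest reply is that Section 19 is a monitoring and regulatory plan. Nothing in it says that the published harms summary will be drawn from the log alone. That stands, and the point is worded accordingly. But no other section provides a different source or a by-arm summary.

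Second, much physical harm is captured elsewhere. Falls are counted whatever their cause, injurious falls have their own analysis, and deaths during the intervention are reported. Complaints that resolve with treatment count as moderate, so they enter the log if possibly related. A data and safety monitoring committee reviews safety after the first 45 men have trained for 3 months. All of this stands. Apart from the falls analyses, it is oversight and does not compare arms.

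Third, pain (Brief Pain Inventory) and fatigue are measured in every arm at baseline, 3, 6 and 12 months with no attribution filter (Sections 3.0 and 8.0). This covers part of the ground, although Section 3.0 plans those measures as moderators or mediators and not as a harms comparison.

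Fourth, the tracking in Section 10.0 can coexist with not formally logging mild events: one is operational, the other regulatory. That is a fair reading, but the record that would carry out the tracking is still unnamed.

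A reader might also infer that a man's own attribution decides what enters the log. The text does not say so. Self-attribution is one of two triggers for optional follow-up of a survey report. The investigator evaluates each event, events can also be raised in class or at testing visits, and a possible link is enough for entry.

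**Conclusion.** The point holds as a minor weakness in harms reporting. It rests on the wording of Sections 19.1, 19.2 and 13.0 and needs no assumed rate. The tabulated record omits the mild harms that the protocol expects, is filtered on relatedness in unblinded men, and is not planned for comparison by arm. Efficacy inference, sample size and regulatory reporting are unaffected.

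Three stronger readings are not supported. One is that mild harms go uncollected: the survey runs monthly in all arms, so the demonstrable gap is in logging and tabulation. Another is that the log will be biased towards a particular arm: the documents give no event rates or attribution rates, so neither a direction nor a size can be stated. The third is that a by-arm table would make the trial able to detect differences in harm: the half-widths of about 12 to 14 points (assuming 30% to 50% of men report an event) and the dilution from unrelated events show that it would describe harms, with wide intervals.

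**What to change.** - Keep all Adverse Events Survey responses, mild ones included, in the analysis data set.
- In Section 13.0, add a table by randomised arm, among all men randomised, of the number and proportion reporting any event in months 1-6, whatever its grade or attribution. Give risk differences with 95% confidence intervals. Show survey months returned by arm, since Section 8.0 stops data collection for men withdrawn as ineligible. Treat months 7-12, after supervised classes end, as descriptive.
- In a second table, show graded exercise-related events by arm, including mild ones where the survey captures them, labelled as subject to unblinded attribution. Section 19.1 defines grades only for exercise-related events, so the first table cannot be graded.
- Name the record that carries out the tracking promised in Section 10.0.
- Optionally, compare Brief Pain Inventory scores by arm in the mixed model already planned for Aim 2.

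The cost is SAP wording and two tables, plus coding time if survey answers are free text. No new visit or instrument is needed. The downsides should be stated in the report: any-cause counts include unrelated events and dilute differences, intervals are wide, and self-report remains unblinded.

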### **19.3. Guidelines to Stop the Study**

Cardiac events or deaths are very rare in persons engaging in low or moderate intensity exercise, though it is possible that a person with previously undisclosed cardiovascular disease may experience a cardiac event or death during exercise. Regardless of cause, we are required to notify the OHSU IRB within 24 hours if a participant dies during this study. We will stop the study if the IRB instructs us to do so.

### **19.4 Data Safety and Monitoring Committee**

The OHSU Knight Cancer Institute Data and Safety Monitoring Committee (DSMC) is responsible for overall coordination of all aspects of the DSMP. The internal audit team conducts quality assurance audits on all open clinical trials that are not monitored by another source. The DSMC meets once each month to review the audit team's progress and findings and to review significant adverse events (SAE) and/or unanticipated problem (UP) reports, and Interim Analysis reports. The DSMC also reviews a full report of study activity for all local, active clinical trials at the time of continuing review submission including:

- protocol amendments, revisions, consent form revisions
- interim analysis results
- protocol violations
- total number of patients enrolled on-study as compared to expected numbers
- dates of patient enrollments
- vital and study (on or off-study) status of each patient
- all Unanticipated Problems submitted (including dates, description and relationship)

Members receive this information approximately one week prior to Committee meetings, to allow for preliminary study and review. The Committee will vote to approve, conditionally approve (enrollment may continue after satisfactory response by the principal investigator to DSMC is

received), suspend or close each protocol reviewed. The Committee decision will be documented in monthly meeting minutes. Principal investigators may appeal the decision to the Director of the Cancer Institute.

The DSMC oversees the process of serious adverse event reporting to assure that reporting requirements are met. The DSMC may require amendments, suspend or terminate any clinical trial that falls within its jurisdiction. The DSMC has the authority to report directly to the OHSU IRB. The DSMC communicates with and provides semi-annual summary reports to the Knight Cancer Regulatory Committee.

The DSMC is made up of the following representatives: physician members of OHSU Knight Cancer Institute, administrators of Clinical Research Management (CRM), biostatistician, research pharmacist, research nurses, and study coordinators. A term of membership is 5 years. In the event that a Committee member is key personnel (principal investigator, co-investigator, biostatistician, study coordinator, study investigational pharmacist, study nurse) for a study under review, or has any other conflict of interest (including substantial financial interest in the study sponsor agency), that member must abstain from Committee review and discussion and must leave the room prior to final decisions on the study. In the event that the Chair is the principal investigator for the study, the Co-Chair of the Committee will oversee the Committee deliberations and final decisions. The Knight DSM Committee includes multiple MD representatives as well as an alternate biostatistician for cases in which our primary biostatistician has a conflict of interest.

## **20.0 INCLUSION OF WOMEN, MINORITIES AND CHILDREN**

Women will be excluded from this study because this study is in prostate cancer survivors only. No men from racial or ethnic groups will be excluded if they meet the criteria for enrollment in the study.

The projected gender, racial and ethnic composition of the study will include a higher proportion of African American men than state demographics because the prostate cancer disproportionately affects African Americans.

**Table 1: Population Demographics - Oregon (%)**

Ethnic Category	Sex/Gender		
	Females	Males	Total
Hispanic or Latino			11.7
Not Hispanic or Latino			88.3
Ethnic Category: Total of all subjects*	100*		
Racial Category			
American Indian or Alaskan Native			1.4
Asian			3.7
Black or African American			1.8
Native Hawaiian or other Pacific Islander			0.3
White			83.6

Ethnic Category	Sex/Gender		
	Females	Males	Total
More than one race			3.8
Unknown/Other			5.3
Racial Category: Total of all subjects*			100*
TOTALS	50.4	49.6	100*

**Source:** U.S. Census Bureau, 2010 \*Totals may not equal 100 due to rounding.

